### 6.3 Secondary endpoint analyses

Secondary endpoints will be compared using t-tests for continuous variables and chi-square tests for dichotomous variables. Feasibility and tolerability of nVNS will be assessed binary as "reached" or "not reached". Overall survival in the first 90 days will be assessed using a Kaplan-Meier estimator. See table for the method of analysis of the other secondary endpoints. For all secondary analyses, no adjustments will be made unless age, NIHSS at randomization and/or baseline infarct core on CTP appear to be unbalanced between the two treatment groups. Effect estimates are expressed as MD or (common) odds ratios (OR) with 95% confidence intervals (CI).

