#### 3.2 Randomization

150 patients are randomized on a 1:1 basis to nVNS on top of best medical practice or best medical practice alone (including intravenous thrombolysis (IVT) and/or endovascular treatment (EVT)). Randomization is performed with Castor (castoredc.com) and is without stratification.

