#### 3.3 Blinding

Patients and investigators are not blinded to treatment allocation due to the nature of the intervention. The primary endpoint will be assessed by two experienced neuroradiologists who are blinded to treatment allocation. The 90-day modified Rankin Scale (mRS) will be assessed by a trained research nurse blinded to treatment allocation.

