#### 6.2 Primary endpoint analysis

Linear regression analysis will be performed to assess the mean difference (MD) in the final infarct volumes between the two groups with corresponding 95% confidence intervals (CIs). The analysis is based on the intention-to-treat principle. Given the randomized design of the study no adjustments for potential outcome variation will be done with multivariable regression analysis. This decision was made after protocol publication. Instead, a sensitivity analysis will be performed with age, NIHSS at randomization and baseline infarct core on CTP as pre-specified covariates.

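### Secondary endpoints are adjusted only if baseline covariates look unbalanced, so the model, the error rate and the meaning of the odds ratios depend on chance

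*SAP*

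**What the plan says.** SAP section 6.3 sets a single rule for the secondary endpoints: "no adjustments will be made unless age, NIHSS at randomization and/or baseline infarct core on CTP appear to be unbalanced between the two treatment groups". Its scope is general: "For all secondary analyses, no adjustments will be made unless" such an imbalance is seen. The section's default tests are t-tests and chi-square tests. The Table at the end of the SAP lists regression models: binary logistic for the penumbra endpoint and for seizures or headache, ordinal logistic for the 90-day mRS, and linear for HADS, EQ-5D/EQ VAS and TICS.

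The primary endpoint is handled differently. Section 6.2 fixes an unadjusted analysis, citing the randomized design, and adds that "a sensitivity analysis will be performed with age, NIHSS at randomization and baseline infarct core on CTP as pre-specified covariates". So the same three covariates are used in a fixed way for the primary endpoint and in a data-dependent way for the secondary endpoints.

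Section 3.2 states that "150 patients are randomized on a 1:1 basis to nVNS on top of best medical practice or best medical practice alone" and that "Randomization is performed with Castor (castoredc.com) and is without stratification". Balance on the three covariates is therefore left to chance. Section 6.1 describes baseline summaries only and gives no criterion for imbalance.

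**The concern.** In a randomized trial a baseline difference between arms is chance. A covariate deserves a place in the model because it predicts outcome, and that can be decided before any data are seen. Choosing the model from the observed imbalance has three consequences.

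- **Error rates.** The unadjusted test has its nominal 5% only when averaged over all draws, balanced and unbalanced. Its false positives come disproportionately from draws in which a prognostic covariate is unbalanced. The rule replaces the test in those draws and keeps it in the balanced ones, where its standard error is too large. The combined procedure falls below 5%, the intervals are too wide when the arms look alike, and power is lost.
- **Meaning of the estimate.** Odds ratios are non-collapsible: adjusted and unadjusted odds ratios are different quantities even with perfect balance. Which one is reported for mRS, penumbra and seizures or headache would depend on the draw.
- **Discretion.** The trigger is a matter of appearance, with no metric. Section 3.3 states that "Patients and investigators are not blinded to treatment allocation due to the nature of the intervention", and section 8 allows a preliminary analysis at soft-lock by the same two analysts who do the final one. Nothing requires the balance judgement to be made before outcomes by arm are seen.

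**Working it through.** The SAP gives no effect size, SD, event rate or power for the secondary endpoints, so there is no stated figure to reproduce.

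**Inputs from the SAP:** 150 patients, 1:1 (taken as 75 per arm), no stratification (3.2); three candidate covariates (6.3); model types (Table).

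**Assumptions:** two-sided 5%, consistent with the 95% intervals; the definition of the trigger; the joint R² of the covariates (0.2 to 0.6); the logit-scale SD of the prognostic score (1 to 2); standard-normal covariates.

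**1. How often adjustment is triggered.** The standard error of a standardized difference is √(2/75) = 0.163. For a cut-off s, the chance that one covariate exceeds it is p = 2[1 − Φ(s/0.163)]. For three independent covariates, the chance of at least one is 1 − (1 − p)³.

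| Trigger | p, one covariate | At least one of three |
|---|---|---|
| p<0.05 | 0.050 | 1 − 0.950³ = 14% |
| difference >0.25 | 0.126 | 1 − 0.874³ = 33% |
| difference >0.2 | 0.221 | 1 − 0.779³ = 53% |
| difference >0.1 | 0.540 | 1 − 0.460³ = 90% |

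**2. Type I error, linear endpoints.** Simulation under no effect, 6,000 trials per cell, adjusting only for covariates that trigger. The Monte Carlo standard error near 5% is √(0.05 × 0.95/6000) = 0.3 percentage points. Ranges cover covariate correlations of 0 and 0.4.

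| Joint R² | p<0.05 | >0.25 | >0.2 | >0.1 | Never adjust | Always adjust |
|---|---|---|---|---|---|---|
| 0.2 | 4.3-4.4% | 4.3% | 4.1-4.2% | 4.1-4.4% | 4.9-5.2% | 4.9% |
| 0.4 | 3.6-3.7% | 3.1% | 2.8-3.0% | 3.1-3.9% | 4.6-5.1% | 4.8-5.1% |
| 0.6 | 2.8-3.2% | 2.2-2.4% | 2.0-2.6% | 2.1-3.4% | 4.5-4.9% | 5.2% |

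Both fixed strategies hold about 5%; the conditional rule does not. Logistic simulations (3,000 trials per cell, standard error 0.4 points) gave 2.5-4.7% under the rule, 3.7-5.1% never adjusted and 4.4-5.8% always adjusted. The direction is the same but the runs are noisier.

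**3. Power, linear endpoints.** Effect of 0.46 SD, chosen so that the unadjusted test has about 80% power; independent covariates.

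| Joint R² | Never | Rule, p<0.05 | Rule, >0.2 | Always |
|---|---|---|---|---|
| 0.2 | 80% | 80% | 82% | 87% |
| 0.4 | 80% | 82% | 86% | 95% |
| 0.6 | 80% | 82% | 89% | 99% |

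**4. If the open trigger is used selectively.** Taking the smallest p-value among the unadjusted, the two rule-based (p<0.05, >0.2) and the fully adjusted analyses gives type I error of 7.3%, 8.2% and 9.0% at R² 0.2, 0.4 and 0.6.

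**5. Change in the odds ratio.** Let logit P(event) = Z + log(2) × treatment, with Z normal, mean 0 and SD σ. Integrating over Z in each arm and forming the odds ratio of the averaged risks gives an unadjusted odds ratio of 1.78 at σ = 1, 1.63 at σ = 1.5 and 1.52 at σ = 2, against 2.0 conditional on Z.

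**The case against.** The strongest reply is that the rule does little harm. The candidate covariates are named in advance in an SAP finalized before database lock, imbalance is judged on baseline data and not on outcomes, and only secondary endpoints are touched. Applied mechanically, the rule errs on the conservative side, so it does not create false positives. The size also depends on things the SAP does not state. If all three covariates enter once any one triggers, type I error is 4.5-5.0% at R² 0.2, 3.9-4.5% at 0.4 and 3.8-4.6% at 0.5. At R² of 0.05-0.1 it is close to nominal under either reading (about 4.2-5.3%). The odds-ratio contrast is an upper bound: if only one of three equally strong covariates enters, the target moves from 1.78 to 1.83, 1.63 to 1.71 or 1.52 to 1.60. Mean differences keep the same target whatever the model. Loss of precision without adjustment applies to any unadjusted analysis, including the primary one.

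These points are right and limit the size. They do not make the rule valid. That the figures vary so much with the reading of the rule shows that the rule is not fixed. Naming the covariates does not settle when they enter, or which. A conservative error still means intervals that are too wide, and it stays conservative only if the trigger is applied mechanically, which the wording does not secure. Open-label allocation does not itself alter the baseline comparison; it matters only because nothing separates the balance judgement from knowledge of outcomes by arm.

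**Conclusion.** The concern holds. Section 6.3 states a data-dependent adjustment rule with an undefined trigger, and no other part of the SAP cures it. The chance that it fires lies anywhere from 14% to 90% depending on how imbalance is read. Followed mechanically with only the triggering covariates entered, it takes type I error for linear endpoints from 5% to about 4.1-4.4% at R² 0.2 and 2.8-3.9% at R² 0.4. At R² 0.4 it gives 82-86% power where always adjusting gives 95%. For the three odds-ratio endpoints, the reported quantity depends on the randomization draw. Inflation to 7-9% arises only if the open trigger is used to choose among results; the SAP does not rule this out, and nothing here suggests that it is intended.

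The sizes rest on assumed prognostic strength, independent or moderately correlated covariates and 75 per arm. They shrink towards nothing if the covariates predict a given endpoint only weakly. The primary analysis is fixed and unaffected, so this is a change that should be made rather than a threat to the main result.

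**What to change.** Delete the conditional clause in section 6.3. State instead that every regression model in the Table is adjusted for age, NIHSS at randomization and baseline CTP core, whatever the observed balance, with the unadjusted estimate reported alongside. Label each odds ratio as adjusted (conditional) or unadjusted.

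If the team prefers to keep the stance of section 6.2, making every secondary analysis unadjusted with a fixed adjusted sensitivity analysis would also remove the data-dependence, but it forgoes the gain in power as the main result.

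The cost is one sentence and no new data. The one technical caveat is the seizures-or-headache model: if events are few, three covariates may call for a penalized logistic fit, which should be named in advance.

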## 7 Missing data and death

For all variables the proportion of missing values will be reported. For the primary endpoint, missing infarct volumes among those patients who are alive on day 5 will be imputed using a model containing the following information: NIHSS at randomization, baseline infarct core volume on CTP, infarct volume on NCCT on day 3 (if available), infarct volume on NCCT on day 5 (if available instead of MRI), treatment with IVT and/or EVT, TICI score post EVT, discharge before day 5, and death after day 5. We will use multiple imputation to generate 10 imputed datasets.

In case of missing questionnaires, these patients will be excluded from analyses on secondary endpoints regarding 90 day follow up. Furthermore, a subanalysis using the lowest and the highest values on the various scales will be conducted.

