# 5 Trial endpoints

#### 5.1 Primary endpoint

Infarct volume on day 5 on MRI among those who are alive.

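### The primary analysis relies in part on imputed day-5 infarct volumes, and no planned analysis tests the assumption behind the imputation

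*SAP*

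**What the plan says.** The primary endpoint (SAP section 5.1) is "Infarct volume on day 5 on MRI among those who are alive". Section 6.2 analyses it without adjustment: "Linear regression analysis will be performed to assess the mean difference (MD) in the final infarct volumes between the two groups". For survivors without a day-5 volume, section 7 says that "missing infarct volumes among those patients who are alive on day 5 will be imputed using a model containing the following information", and plans 10 imputed datasets. The list starts with NIHSS, baseline CTP core, and NCCT volumes on day 3 and day 5 where they exist. It ends with "treatment with IVT and/or EVT, TICI score post EVT, discharge before day 5, and death after day 5". Treatment arm is not on it.

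For the primary endpoint, section 6.2 names one sensitivity analysis: "a sensitivity analysis will be performed with age, NIHSS at randomization and baseline infarct core on CTP as pre-specified covariates". Section 7 does plan an extreme-value check, "a subanalysis using the lowest and the highest values on the various scales will be conducted", but in the paragraph on missing 90-day questionnaires, so it does not reach infarct volume. On the extent of missing data, section 7 promises the proportion missing for every variable and says nothing on whether this is split by arm or by reason. Section 3.3 states that "Patients and investigators are not blinded to treatment allocation due to the nature of the intervention".

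**The concern.** Standard multiple imputation is unbiased only if patients without a day-5 MRI have, given the listed predictors, the same distribution of infarct volume as those with one. The SAP does not state this assumption, and nothing it plans for the primary endpoint departs from it.

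Two features make a departure worth examining. The predictors include early discharge and later death, which suggests that scans may be lost among both the mildest and the most severely affected patients. The trial is also open label, so whether a scan is obtained could depend on arm. Blinded reading protects the volumes that are measured, but not those that never were.

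If unscanned nVNS patients had larger infarcts than the model predicts, and controls did not, the mean difference would be biased in favour of nVNS. The reverse pattern would hide a benefit. Followed as written, the plan gives an imputed estimate and a covariate-adjusted one, and neither shows how far the conclusion depends on the assumption. The questionnaires get such a check. The endpoint on which the trial's conclusion rests does not.

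**Working it through.** The SAP states no SD, target effect, power or expected missing rate, so there is no figure of the plan's own to reproduce. The check is an illustration, and its assumed inputs are marked as such.

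**Inputs**
- From SAP section 3.2: "150 patients are randomized on a 1:1 basis to nVNS on top of best medical practice or best medical practice alone", so 75 per arm.
- Assumed: SD of day-5 volume 50 mL (range 40-60).
- Assumed: fraction f of volumes missing in the affected arm, 10-25%.
- Assumed: departure δ (true minus imputed mean among the missing), 10-30 mL in one arm and zero in the other.

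**Standard error of the mean difference**, SD × √(2/75):
- SD 40: 6.5 mL
- SD 50: 8.2 mL
- SD 60: 9.8 mL

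This ignores deaths before day 5 and the extra variance from imputation. Both would raise the SE and so slightly lower the ratios below.

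**Size of the shift.** The true and the estimated mean difference differ by f(nVNS) × δ(nVNS) − f(control) × δ(control). With a departure in one arm only, this is f × δ. The last column starts from an assumed borderline result, z = 2.2 (p = 0.028), and moves it towards zero.

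| f | δ (mL) | shift (mL) | shift/SE at SD 50 | p becomes |
|---|---|---|---|---|
| 0.10 | 10 | 1.0 | 0.12 | 0.038 |
| 0.15 | 20 | 3.0 | 0.37 | 0.067 |
| 0.25 | 30 | 7.5 | 0.92 | 0.20 |

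Across SD 40-60 mL the ratio runs from 1.0/9.8 = 0.10 to 7.5/6.5 = 1.15 SE. If both arms share the same departure, only the difference in missing fractions counts. For example, 20% against 10% missing with a 1.0 SD departure gives 0.10 SD.

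**Can it hide an effect?** In SD units the SE is √(2/75) = 0.163, and 80% power corresponds to a difference of 0.457 SD. With a one-arm departure of 0.5 SD working against the effect:
- 10% missing: bias 0.05 SD, power falls to 70%.
- 20% missing: bias 0.10 SD, power falls to 59%.

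**Can it create an effect from zero?** The 95% half-width is 1.96 × 0.163 = 0.320 SD. The one-arm departure that moves a zero estimate to that boundary is 0.320/f:
- 5% missing: 6.4 SD
- 10% missing: 3.2 SD
- 20% missing: 1.6 SD (80 mL at SD 50)
- 30% missing: 1.07 SD

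The largest shift in the table, 0.92 SE, is below 1.96 SE. Two-sided false-positive risk rises from 5% to about 6.6% in the middle row and about 15% in the last.

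**Treatment arm left out of the imputation model.** If the section 7 list is complete and no listed predictor carries the treatment effect, the imputed patients contribute no difference between arms. The estimate then shrinks by a factor of about 1 − f, that is 0.90, 0.80 and 0.70 at 10%, 20% and 30% missing in both arms. A simulation with one baseline predictor correlated 0.7 with outcome gave 0.91, 0.79 and 0.71. NCCT volumes, being post-randomisation, could carry part of the effect and reduce this.

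**The case against.** The strongest defence is the imputation model itself. Where a day-5 NCCT exists, it measures the same lesion on the same day. The day-3 NCCT, NIHSS, CTP core, reperfusion variables, early discharge and later death cover much of what separates unscanned from scanned patients. The departure δ is what remains after these. If predictors and outcome correlate at 0.8-0.9 (assumed), the residual SD is about 30-22 mL, so a 30 mL average departure in one arm alone would be 1.0-1.4 residual SDs, which is large. At a correlation of 0.6 it is 0.75. This stands: the upper end of the illustrated range is demanding, and every input to it is assumed. But good predictors make the assumption more credible without testing it, and the NCCT volumes enter only where available.

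Several stronger readings are tempting, and the document does not support them:
- That the plan could produce a significant result out of nothing. Only the missing volumes are imputed, and the arithmetic shows how extreme the loss would have to be.
- That missingness will be reported only overall. Section 7 is silent on arm; it does not exclude it.
- That scan loss does differ by arm. Open-label treatment makes this possible, and no passage indicates that it happens.
- That the adjusted sensitivity analysis uses the same imputed volumes. Section 6.2 does not say. Either way, covariate adjustment is not designed to examine non-random loss.

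It may also be said that the SAP states nothing false here. That is so: the matter is an omitted robustness check. But the SAP's introduction names missing-data handling among the details it is there to supply, and section 8 allows a preliminary analysis at soft-lock. A check chosen after that would be chosen with results in view.

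**Conclusion.** The point holds as a worthwhile, inexpensive improvement; it does not invalidate the primary analysis. Part of the primary result will come from volumes imputed under an assumption that the plan neither states nor probes, in an open-label trial where loss at both ends of severity is plausible. Under the assumed inputs the effect on the mean difference is 1.0-7.5 mL (0.12-0.92 SE at SD 50 mL). That is enough to tip a borderline result or mask a modest effect. By itself it is unlikely to turn a zero estimate into a significant one, unless about 20% or more of the volumes are missing and the departure in one arm is large. If few MRIs are missing, the concern becomes small: at 5% missing and a departure of up to 1.0 SD, the bias is at most 0.05 SD.

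The absence of treatment arm from the imputation list belongs to the same point. Read literally, it pulls the estimate towards no difference, and any sensitivity analysis built on that model would start from a biased reference.

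**What to change.** Keep multiple imputation as the primary analysis and amend sections 6.2 and 7 as follows.

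1. Add treatment arm to the imputation model, and state the missing-at-random assumption.
2. Pre-specify a delta-adjusted (tipping-point) analysis. Add a fixed amount to the imputed volumes, separately by arm, for example −30 to +30 mL in 10 mL steps, widened if needed. Report the delta at which the conclusion changes. State how shifted volumes below zero are handled.
3. Pre-specify a regression on available MRIs as a supporting comparison. It rests on its own missingness assumption, so it does not replace item 2.
4. Report missing day-5 MRIs by arm and by reason (discharged, too unwell, refused, other).

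The cost is SAP wording, some code and a slightly longer results section. No further patients or measurements are needed, though the reasons for missing scans must be on record. The downside is that the primary conclusion may look less firm.

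### The imputation model for the primary endpoint omits randomised arm, so the estimated difference in infarct volume is pulled toward zero; age is missing from it too

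*SAP*

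**What the plan says.** SAP section 7 states that volumes missing in survivors to day 5 "will be imputed using a model containing the following information: NIHSS at randomization, baseline infarct core volume on CTP". The list continues with the NCCT volume on day 3 and on day 5 where these exist, and then "treatment with IVT and/or EVT, TICI score post EVT, discharge before day 5, and death after day 5". The method is fixed as well: "We will use multiple imputation to generate 10 imputed datasets". The section does not say that imputation is done separately by arm.

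SAP section 6.2 defines the analysis that these data feed: "Linear regression analysis will be performed to assess the mean difference (MD) in the final infarct volumes between the two groups". It has no covariates, and "The analysis is based on the intention-to-treat principle". It also announces that "a sensitivity analysis will be performed with age, NIHSS at randomization and baseline infarct core on CTP as pre-specified covariates".

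The only treatment on the section 7 list is IVT and/or EVT. Section 3.2 makes these part of best medical practice, which both groups receive, so they do not stand in for nVNS.

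**The concern.** An imputation model should contain every variable of the analysis model. Here it lacks the one variable whose coefficient is the trial's primary result. Imputed volumes then carry no treatment effect of their own. They carry only the part that passes through listed variables measured after randomisation, such as the NCCT volumes. Mixing these values with the observed ones moves the mean difference toward zero and lowers power.

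Nothing else in the plan would show this. The sensitivity analysis in section 6.2 adds covariates but does not change the imputation. No complete-case or alternative imputation analysis of the primary endpoint is specified. If the age-adjusted analysis uses the same imputed data, which section 6.2 does not say, it inherits the omission of arm and also adjusts for a variable absent from the imputation.

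The SAP itself expects missing MRI: section 7 lists discharge before day 5, and NCCT done in place of MRI, as predictors.

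**Working it through.** **Inputs from the SAP.** 150 patients randomised 1:1, so 75 per arm (section 3.2); unadjusted mean difference by linear regression (6.2); 10 imputed datasets and the listed predictors (7). The SAP gives no effect size, SD, power or expected missing rate, so there is no stated figure to reproduce.

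**Assumptions.** 10, 20 or 30% of volumes missing (150 × 0.10, 0.20, 0.30 = 15, 30, 45 patients) and a normally distributed outcome in SD units. True difference δ = 0.5 SD. Baseline core correlates 0.5 with outcome. Data are missing completely at random. The CT volume is either absent for everyone, or present for everyone with correlation r = 0.6 or 0.9 to the MRI volume within arm.

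**Step 1: no CT volume.** The baseline predictors are balanced by randomisation. With arm left out, the imputed volumes have the same expected mean in both arms. With missing fraction m:

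expected difference = (1 − m) × δ + m × 0 = (1 − m) × δ

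The share kept is therefore 90%, 80% and 70%.

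**Step 2: CT volume available.** Let λ be the share of the effect that CT carries into the imputed values. The share kept is 1 − m(1 − λ). Given baseline core, the outcome variance pooled over arms is 0.75 + 0.25 × 0.5² = 0.8125, so

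λ = 0.8125 r² / (0.8125 r² + 1 − r²)

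- r = 0.6: λ = 0.2925 / (0.2925 + 0.64) = 0.314. Share kept: 93%, 86%, 79%.
- r = 0.9: λ = 0.6581 / (0.6581 + 0.19) = 0.776. Share kept: 98%, 96%, 93%.

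**Step 3: simulation under these assumptions.** 1,500 trials per scenario, Bayesian linear-regression imputation, 10 imputations, Rubin's rules. Power with no missing data is 0.86.

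| Missing | CT volume | Share of true difference kept, arm omitted | Power, arm omitted | Power, arm included |
|---|---|---|---|---|
| 10% | none | 90% | 0.77 | 0.85 |
| 10% | r 0.6 | 93% | 0.81 | 0.85 |
| 10% | r 0.9 | 98% | 0.85 | 0.86 |
| 20% | none | 80% | 0.63 | 0.79 |
| 20% | r 0.6 | 86% | 0.71 | 0.81 |
| 20% | r 0.9 | 96% | 0.82 | 0.84 |
| 30% | none | 70% | 0.46 | 0.76 |
| 30% | r 0.6 | 78% | 0.61 | 0.77 |
| 30% | r 0.9 | 94% | 0.81 | 0.83 |

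The simulation agrees with the formulas. With arm included, the estimate is 99–101% of the truth in every row. Complete-case analysis was also unbiased under these assumptions, so imputation as written can be worse than none. With arm omitted and no CT volume, the pooled standard error at 20% missing averages 0.179, while the estimate actually varies with SD 0.152. The interval is therefore too wide around an estimate that is too small.

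**Step 4: other assumptions.** With a true difference of 0.4605 SD (80% power with complete data), other predictors explaining 40% of variance, data missing at random and 2,000 trials per rate, the mean estimate without arm is 0.412, 0.368 and 0.321. Divided by 0.4605, this is 89%, 80% and 70%. Power is 70, 55 and 40%, against 77, 74 and 68% with arm. Coverage at 30% missing is 92%. A CT volume with r about 0.8 for everyone keeps 95, 90 and 86%.

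**Step 5: age.** Simulated with age predicting both outcome and missingness (true difference 0.4605 SD), leaving out age alone gives 0.461, 0.470 and 0.464 at 10, 20 and 30% missing. There is no shrinkage.

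**The case against.** Five points can be made for the plan.

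- **CT volumes protect the estimate.** The day-3 NCCT feeds a secondary endpoint (section 5.2), so it should exist for many patients. This stands in part: with a closely correlated CT volume the loss is only 2–6%, and the no-CT figures are the unfavourable end of the range. But section 7 uses these volumes only where available, and a patient discharged early may lack both the MRI and the CT.
- **The error is conservative.** With no true effect, the estimate stays unbiased and rejection is 3.1, 2.5 and 1.5% at a nominal 5% for 10, 20 and 30% missing. Coverage is near nominal up to 20% missing. This stands: the harm is an understated or missed effect.
- **Age does not cause the bias.** This stands (step 5). Age belongs in the model because an imputation model should contain the variables of each analysis it serves, and because it helps make missing-at-random plausible.
- **The list may not be exhaustive.** Section 7 does not say that only these variables are used, and analysts might include arm anyway. This is weak. The list is detailed, the introduction names missing-data handling as something this SAP specifies, and adding arm would go beyond what it records.
- **Every figure rests on assumptions.** True. If few MRIs are missing, the bias is small, since the loss is at most about the missing fraction. The direction does not depend on the rate.

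**Conclusion.** The concern holds. The imputation model as written omits randomised arm, and the primary mean difference is then biased toward zero. The proportional loss is roughly the missing fraction when no CT volume is available, and smaller when one is: at 20% missing, 80% of the true difference is kept without CT, and 86–96% with a CT volume correlating 0.6–0.9. Power at that rate falls from 0.79 to 0.63 without CT, and from 0.81–0.84 to 0.71–0.82 with it. These sizes assume a 0.5 SD effect, a normal outcome and volumes missing completely at random; none of this is in the SAP. The omission of age is a lesser defect that concerns the sensitivity analysis. Because the error affects the primary estimate in a known direction and costs almost nothing to remove, it should be corrected.

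**What to change.** In SAP section 7, add randomised treatment arm and age to the imputation model, or impute separately by arm with age included. State that the model contains all variables of both the primary and the sensitivity analysis in section 6.2. The change should be in writing before the preliminary analysis that section 8 allows after the soft-lock. It costs one sentence and needs no new data and no extra patients.
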